# 8.4. Removal of Patients from Study

Withdrawal of a patient from the study means that no further study visits or procedures are performed and no further data are collected. Every reasonable effort will be made to keep the patient in the study; however, in the event that a patient is withdrawn from the study, every effort will be made by the investigator to complete and report the reasons for withdrawal as thoroughly as possible. The reason for termination must be clearly documented on the appropriate page of the eCRF. Study withdrawal should include the final assessments, as required by the protocol and every effort should be made to perform the study follow-up procedures (e.g., laboratory tests, physical examination including an evaluation of toxicity/adverse events). Refer to Table 1 and

Timepoint (Study Day)	Cycle 26	Cycle 28	Cycle 30	Cycle 32	Cycle 34	Cycle 36+		30-Day	
	Day 1 (± 3d)	Day 1 (± 3d)	Day 1 (± 3d)	Day 1 (± 3d)	Day 1 (± 3d)	Day 1 (± 3d)	EOS Tx 	FU  (± 5d)	UNS k
Physical Examination a	Х	Х	Х	X	Х	Х	Х	Х	X
Neurological Examination b	Х	Х	X	X	X	X			X
Vital Signs c	Х	Х	Х	X	X	X	X	Х	X
Safety Labs d	Х	Х	Х	X	X	X	X	Х	X
12-Lead ECG e	Х	Х	Х	X	Х	X	X		X
Disease Assessment f	Х	Х	Х	Х	X	Х	Х		X
Karnofsky performance status	X	X	X	X	X	X	Х		X
Corticosteroid use	X	X	X	X	X	X	Х		X
MRI tumor assessment	Х	Х	X	X	X	X	Х		X
Concomitant Medications	X	X	Х	X	X	X	Х	Х	X
Tesevatinib Dispensing g	Х	Х	Х	Х	X	Х			X
AE Monitoringh	X	X	X	X	X	X	Х		Х

Table 2b:Schedule of Study Assessments for Subjects Completing 24 Cycles of TesevatinibTreatment

d = day; ECG = electrocardiogram; EOS = end of study; FU = follow-up; KPS = Karnofsky Performance Status; LTFU = long-term follow-up; MRI = magnetic resonance imaging; PK = pharmacokinetic; UNS = unscheduled; Tx = treatment

1: Abbreviated PE is acceptable (to be completed in a targeted manner covering related body systems).

m: Neurological exam should include full cranial nerve central and peripheral, motor and sensory assessments.

n: Vital sign measurements (blood pressure, heart rate, respiratory rate, and temperature) to be obtained with patient in sitting position.

o: To be drawn and analyzed locally. Safety labs = hematology and clinical chemistry. See Table 2b.

p: Supine 12-Lead ECGs will be performed at each visit.

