### Table 3.

A termination eCRF must be completed for all enrolled patients.

The patient may be withdrawn from the study for any of the following reasons.

- Voluntary withdrawal by patient
- Patient lost to follow-up
- Termination of the study by sponsor
- Patient death

If a patient dies, Kadmon will actively seek to determine the date and cause of death.

If there is an ongoing toxicity associated with tesevatinib, patients must be followed with appropriate medical management until resolution or stabilization.

A reasonable effort should be made to contact any patient who is lost to follow-up during the course of the study in order to complete assessments and retrieve any outstanding data. If a patient is unreachable by telephone after three (3) attempts, the minimum of a registered letter should be sent requesting that the patient make contact with the investigator.

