### 9.1.3.2. Study Drug Discontinuation

Withdrawal of a patient from study treatment means that no further tesevatinib is administered but the remaining study visits or procedures are performed and follow-up data are collected.

A patient's study drug may be prematurely discontinued for any of the following reasons:

- Progression of disease
- An AE requires permanent discontinuation of study drug
- Voluntary withdrawal by patient
- Protocol deviation
- Patient lost to follow-up
- Patient death
- Termination of study by sponsor

Patients that have study drug discontinued due to toxicity are to be followed until there is either:

- Resolution or stabilization to baseline or Grade 1
- The patient is lost to follow-up
- The event is otherwise explained

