### Grade 4 QTc(F) Prolongation:

If the QTc(F) interval increases to an absolute value of  $\geq 500$  msec at any evaluation, and if the patient is or has recently been symptomatic (has palpitations, dizziness, syncope, orthostatic hypotension, a significant ventricular arrhythmia on ECG), then the following actions should be taken:

- The patient should be hospitalized and undergo a thorough cardiology evaluation
- Do not dose with study drug again
- Consult with Medical Monitor
- Check electrolytes especially magnesium and potassium; correct abnormalities as clinically indicated

• ECGs should be monitored until the QTc(F) returns to within 30 msec above the average baseline value or  $\leq$  470 msec

Study drug should be permanently discontinued if the cardiac/electrophysiology evaluation confirms that symptoms are the consequence of a drug-induced QTc(F) interval prolongation. However, if the patient has objective tumor response, consideration will be given to continuing treatment with tesevatinib at a reduced dose after discussion with the Medical Monitor.

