### 11.3.10. Pregnancy

If any patient becomes pregnant following the first dose of tesevatinib, the patient will be taken off study and followed regularly until birth or termination of the pregnancy. The pregnancy must be immediately reported to the sponsor. Forms for reporting pregnancies will be provided to the study sites upon request. The anticipated date of birth or termination of the pregnancy should be provided at the time of the initial report. The outcome of a pregnancy must be reported to the Medical Monitor as soon as it is known. If the pregnancy ends for any reason before the anticipated date initially reported, the investigator must notify the Kadmon Medical Monitor as soon as possible.

If the outcome of the pregnancy meets any criterion for classification as a SAE (including stillbirth, neonatal death, spontaneous abortion, or congenital anomaly – including that in an aborted fetus) the investigator must follow the procedures for reporting SAEs. Any neonatal death occurring  $\leq$  30 days after birth will be reported as a SAE.

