## 12.1.9. 12-Lead Electrocardiogram (ECG)

Supine 12-Lead ECGs will be performed at screening; predose, and once within 4 - 8 hours postdose on Days 1 and 15 of Cycle 1; pre-dose on Day 1 of Cycles 2 and beyond; and at the End of Study Drug Treatment visit. ECGs will be read by a central laboratory.

ECGs are to be performed before any blood sample collection when possible.

ECGs are to be repeated three times consecutively within 30 minutes (must have an interval of at least 1–2 minutes between ECGs).

During the study, all ECGs will be digitally analyzed by a validated central ECG laboratory vendor. This central vendor will place ECG machines at sites under contract with Kadmon. ECGs will be transmitted electronically to the central vendor for analysis. Reports, including clinical alerts resulting from the analysis of the ECGs, will be provided back to sites. Sites will be trained on the use of the ECG machines, and instructions for performing ECG assessments will be provided in the ECG manual. Although ECGs will be read by a central laboratory, sites should take action if clinically significant abnormalities are detected at time of ECG.

Subjects who have completed 24 cycles of treatment without disease progression or unacceptable toxicity will have ECG assessments performed at each bi-monthly visit. These ECG assessments will be performed locally and read by qualified site personnel.

Prior to enrollment, all patients must demonstrate an average screening QTc(F) value of  $\leq 470$  msec by central digital analysis. Immediate clinical management of patients will initially be based on results of machine-read ECGs at the sites. However, the central digital analysis will prevail as it becomes available. In addition, the central digital analysis will be used for any AE and SAE documentation.

An increase in QTc(F) interval (by central digital analysis) to a value > 60 msec above baseline or to the level of  $\geq$  500 msec requires further monitoring. After discussion with the Medical Monitor (if  $\geq$  500 msec) on appropriate management, the patient may be removed from the trial (see guidelines in Section 9.1.4.3.1).

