## 12.1.16. Adverse Event Assessments

Information regarding the occurrence of AEs and SAEs will be collected from the time the patient signs the informed consent form throughout their participation in the study, including a period of 30 days after the patient's last dose of study drug, unless a new treatment has been

started. Any known untoward event that occurs beyond the AE reporting period that the investigator assesses as possibly related to tesevatinib also should be reported to Kadmon.

**Note:** AEs resulting in a patient's permanent discontinuation from the study, regardless of seriousness or relationship to study drug, MUST be promptly reported to the sponsor.

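### Sections 12.1.9 (QTcF of 500 msec or more) and 11.3.10 (pregnancy) use study-exit wording; read literally, a progression-free patient could lose the week-24 assessment and be scored a PFS-6 failure

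*Protocol*

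**What the plan says.** The protocol separates two kinds of stopping.

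- **Leaving the study (Section 8.4).** "Withdrawal of a patient from the study means that no further study visits or procedures are performed and no further data are collected". The section adds that "every effort should be made to perform the study follow-up procedures (e.g., laboratory tests, physical examination including an evaluation of toxicity/adverse events"). Its list, introduced by "The patient may be withdrawn from the study for any of the following reasons", has four entries: voluntary withdrawal, loss to follow-up, termination by the sponsor, and death.
- **Leaving treatment (Section 9.1.3.2).** Here "no further tesevatinib is administered but the remaining study visits or procedures are performed and follow-up data are collected". An adverse event that requires permanent discontinuation of drug is one of the listed reasons.

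Two other sections use the language of leaving the study.

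- **QTcF (Section 12.1.9).** For a value of 500 msec or more, following discussion with the Medical Monitor "on appropriate management, the patient may be removed from the trial". The sentence refers the reader to Section 9.1.4.3.1.
- **Pregnancy (Section 11.3.10).** "the patient will be taken off study and followed regularly until birth or termination of the pregnancy". The section does not mention study drug or disease assessment.

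SAP 3.8.1 scores a patient whose 24-week status is unknown as not alive or progression-free. Protocol Section 13.4.6.1 would instead censor such a patient at the last disease assessment, so the failure scoring comes from the SAP.

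**The concern.** Because the protocol defines both terms, choosing one has a consequence. A site that applies 12.1.9 or 11.3.10 as written and then turns to 8.4 could stop MRI in a patient who has not progressed. If that happens before week 24, the primary endpoint is unknown and SAP 3.8.1 turns it into a failure. The data would be lost through wording, not because the patient could not be assessed. At stake is a small, avoidable understatement of PFS-6 in a single-arm trial of 40 patients, where each patient carries visible weight.

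**Working it through.** **Step 1. Does the study-exit wording fit the rest of the protocol?**

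- *QTcF.* It is not an 8.4 withdrawal reason. Section 9.1.4.3.1, to which 12.1.9 points, has only drug actions. For asymptomatic values of 500 msec or more, drug is held and may be restarted at a reduced dose. For symptomatic (Grade 4) cases, "Study drug should be permanently discontinued if the cardiac/electrophysiology evaluation confirms that symptoms are the consequence of a drug-induced QTc(F) interval prolongation". Section 9.1.3.2 already covers an adverse event that ends treatment. So 12.1.9 names a study exit that neither 8.4 nor the cited guidance provides for.
- *Pregnancy.* It is not an 8.4 reason either. Unlike 12.1.9, the wording in 11.3.10 is mandatory, and the only follow-up it names is of the pregnancy.

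**Step 2. Does other text secure the week-24 assessment?**

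- Section 8.4 asks for final assessments and refers to Table 1, whose end-of-treatment column includes MRI. The Table 1 footnotes waive that MRI if one was done in the previous 8 weeks. A single exit scan gives week-24 status only if the exit falls at about week 24.
- Sections 10 and 12.1.10 require 8-weekly assessment until progression for patients who discontinue *treatment*. Section 12.2.12 requires assessment until progression if none was seen before the end-of-treatment visit. These secure the endpoint if the patient counts as off treatment. They conflict with 8.4 if the patient counts as off study. The text does not say which prevails.

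**Step 3. What is one patient worth?**

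Inputs: N = 40, target PFS-6 25%, reference rate 10%, one-sided 5% (Protocol 13.2); Clopper-Pearson limits (SAP 3.1.4.2); unknown counted as failure (SAP 3.8.1).

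*The plan's own figure first.* Protocol 13.2 states 80% power to show a rate above 10%. With a Clopper-Pearson lower 90% limit, the smallest count whose limit exceeds 10% is 8 of 40 (limit 10.4%; at 7 of 40 it is 8.5%). P(X ≥ 8 | n = 40, p = 0.25) = 81.8%, close to the stated 80%, which came from Weibull simulation with a Cox model.

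*Loss per patient.* One success moved to failure costs 1/40 = 2.5 points:

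| Successes | PFS-6 | 95% CI |
|---|---|---|
| 10/40 | 25.0% | 12.7–41.2% |
| 9/40 | 22.5% | 10.8–38.5% |
| 8/40 | 20.0% | 9.1–35.6% |

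*Power, under an assumption.* The documents give no rate of removal. Let q be the share of would-be successes lost this way, so the observed rate is 0.25 × (1 − q). With the threshold of 8 of 40:

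| q (assumed) | Rate | Power above 10% |
|---|---|---|
| 0 | 25.0% | 81.8% |
| 2.5% | 24.4% | 79.3% |
| 5% | 23.75% | 76.7% |
| 10% | 22.5% | 70.6% |

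Ten successes are expected (0.25 × 40), so q = 10% means losing one of them on average. That is probably well above what would occur.

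**Step 4. Direction.** The SAP rule can only move a patient from success to failure. PFS-6 can fall but cannot rise, so no false positive arises.

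**The case against.** The strongest reply is that the protocol, read as a whole, already keeps these patients in follow-up. Removal under 12.1.9 is optional and rests on drug-only guidance. The synopsis says that patients are followed for progression after end of treatment, and Sections 9.1.3.2, 10, 12.1.10 and 12.2.12 agree. The 8.4 follow-up procedures are given only as examples, alongside final assessments that include MRI. This stands as evidence of intent for QTcF, so a reader who infers that the plan *does* end disease assessment goes too far. It does not settle the literal conflict. For pregnancy, 11.3.10 has no pointer to drug-only guidance.

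The affected group is also likely to be tiny. Section 5.2 reports QTc prolongation in approximately 20% of earlier patients with malignancies, mostly Grade 2 and 3 with no Grade 4, on machine-read ECGs; the share at 500 msec or more is not given. Pregnancy is remote given the contraception rules and repeated testing. This stands.

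Three further inferences are tempting, but the documents do not support them.

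- *A loss specific to the day of removal, read off the Weibull curve in Section 13.2.* That curve is the PFS assumed on tesevatinib, and these patients have stopped it. Section 12.2.14 also dates progression to the latest MRI when new anti-cancer treatment starts without progression. A patient so treated before week 24 therefore fails PFS-6 whatever 12.1.9 says.
- *That Section 12.1.16 is a third route out of the study.* It refers to adverse events leading to "permanent discontinuation from the study, regardless of seriousness or relationship to study drug", but it is a prompt-reporting rule and authorises no withdrawal.
- *That Amendment 4's removal of long-term follow-up, or the 30-day period in SAP 2.2, ends imaging.* The synopsis Follow-Up Period text and Sections 10, 12.1.10, 12.2.12 and 12.2.13 still require assessment until progression.

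Finally, SAP 3.8.2.3 plans Kaplan-Meier PFS, which handles patients without an event by censoring. That softens the effect on the PFS summary but leaves the primary endpoint unchanged.

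**Conclusion.** The point holds as a wording conflict with a conditional consequence. Sections 12.1.9 and 11.3.10 use study-exit language that 8.4 defines as ending data collection, and SAP 3.8.1 would score the resulting gap as a failure. The size is at most 2.5 points of PFS-6 for each patient who would have been progression-free at week 24 on no new therapy, and nothing for any other removed patient. This assumes 40 treated patients and a site that reads the wording literally. How many patients would be affected cannot be derived; it is probably very few. The bias runs against the drug. It is a cheap improvement worth making, not a flaw that threatens the trial's conclusion.

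**What to change.** Two edits:

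- **Section 12.1.9:** replace *removed from the trial* with *have study drug discontinued, with disease assessments continuing per 9.1.3.2 and Section 10*.
- **Section 11.3.10:** replace *taken off study* with *have study drug permanently discontinued*, and state that disease assessments continue per Section 10 as far as clinically appropriate in pregnancy. The pregnancy follow-up stays as written.

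The cost is the wording change and a few MRIs after drug is stopped, which the protocol already requires after treatment discontinuation. In pregnancy, imaging may still be limited on clinical grounds, so the second edit reduces the risk of an unknown week-24 status but cannot remove it.

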## 12.1.10. Disease and Response Assessments

Disease assessments will be based on the RANO criteria [Wen 2010] and will comprise radiological assessments (MRI), clinical assessments (KPS), and corticosteroid use. Based on radiological assessments, clinical status, and corticosteroid use, an overall evaluation of CR, PR, SD, or PD should be made at each disease assessment (see Section 10) after baseline according to the RANO criteria (Appendix 2).

Disease assessment during the screening period is to be performed within 7 days before study drug administration and must be used as the baseline radiological assessment. Per the study's schedule of assessments (see Table 1), disease assessment is intended to be done prior to starting cycle 2, 3, 5, 7+. The corticosteroid dose should be kept stable for 5 days prior to the MRI scan. During the study, disease assessments should be performed at week 4 and week 8 after the date of first study treatment and then every 8 weeks thereafter (at Week 16, 24, etc.), regardless of treatment delays. For patients who discontinue treatment for other reasons than PD, disease assessment in the follow-up period should continue every 8 weeks (according to the original schedule) until disease progression. For patients with PD, disease assessment at the EOS is only required if not performed within the previous 8 weeks.

Disease assessments as initially planned according to the schedule of assessments should be maintained regardless of treatment delays. Unscheduled disease assessments may be performed at the discretion of the investigator to allow a decision on further study treatment administration for individual patients. For patients who discontinue treatment for reasons other than progressive disease, disease assessment in the follow-up period should continue every 8 weeks (according to the original schedule) until disease progression.

## 12.1.11. Tesevatinib Administration

Tesevatinib will be administered at the dose of 300 mg once daily. Tesevatinib will be used in dosage strength of 100-mg, and 150-mg tablets. Patient diaries will be utilized to evaluate compliance. One cycle will be defined as 28 days of treatment.

Tesevatinib should be taken in the morning (unless there is a patient-specific rationale to take it regularly at a different time of day) and can be administered without regard to food intake.

## 12.1.12. Patient Reported Outcomes (MDASI-BT)

PROs of disease- and treatment-related symptom severity and symptom interference will be assessed using the MDASI-BT questionnaire.

The MDASI is a validated and reliable self-report measure that was developed to assess symptom severity and interference [Cleeland 2000; Armstrong 2006].

Thirteen items ask patients to rate how severe the symptoms were when "at their worst" in the last 24 hours with regard to pain, fatigue, nausea, disturbed sleep, distress, shortness of breath, remembering things, lack of appetite, drowsy, dry mouth, sad, vomiting, and numbness or tingling. An additional six items ask patients to rate how much the symptoms have interfered with six areas of function (general activity, walking, work, mood, relations with other people, and enjoyment of life) in the last 24 hours. The MDASI-BT (see Appendix 3) contains an additional nine items that assess symptoms and concerns specific to primary brain tumor patients (difficulty understanding, difficulty speaking, difficulty concentrating, seizures, weakness, change in appearance, change in vision, change in bowel patterns, irritability), for a total of 28 items.

All patients will complete the self-administered questionnaire pre-dose on Day 1 of Cycles 1 and 2; every 8 weeks after enrollment (i.e., coinciding with the schedule of disease assessments); and

at the End of Study Drug Treatment visit (EOS). Additionally, patients who discontinue study treatment for reasons other than disease progression will complete the questionnaire every 8 weeks during follow-up until the time of documented disease progression. The questionnaire will take patients  $\sim$ 5–10 minutes to complete. Patients must complete the questionnaire prior to any other tests or assessments and prior to any discussion of the patient's progress with their physician or any other healthcare personnel at the site.

Subjects who have completed 24 cycles of treatment without disease progression or unacceptable toxicity will not be required to complete the MDASI-BT questionnaire at subsequent bi-monthly visits.

## 12.1.13. Tesevatinib Plasma Concentrations

Blood samples will be drawn to evaluate tesevatinib plasma concentrations. Plasma samples for tesevatinib concentration analysis will be drawn predose of tesevatinib on Days 15 of Cycle 1; and predose of tesevatinib on Day 1 of every subsequent cycle (up to cycle 6). Data from these samples will contribute to a population PK analysis, and will be used to explore exposure-response relationships.

#### 12.1.14. Pharmacodynamics

The tumor tissues submitted should be a formalin-fixed, paraffin-embedded tumor specimen that enables the definitive diagnosis of glioblastoma and determination of EGFR status, to permit stratification for the purposes of the efficacy analyses.

A tissue block (preferred) or 20 serial, freshly cut, unstained slides accompanied by an associated pathology report is required for participation in this study. Tissue quality and adequate viable tumor cell content are specified in the accompanying lab manual.

Cytological samples are not acceptable.

For enrolled patients, part of the available tumor tissue from the tissue submitted will be used to assess exploratory biomarkers. Tissue assessments may include testing of protein expression, activation status, somatic mutations, and/or gene amplification of EGFR, and other exploratory markers related to tesevatinib and to glioblastoma biology. These assessments will be performed by the Sponsor, at a central laboratory, or by a Sponsor-selected vendor. The remaining tumor tissue block will be returned to the site.

